6.1 Study treatment

All dosages of study drug prescribed and dispensed to the patient and all dose changes during the study must be recorded on the Dosage Administration Record eCRF.

The investigator or responsible site personnel should instruct the patient to take the study drug as per protocol (promote compliance). Study drug accountability must be performed on a regular basis. Patients will be instructed to return unused study drug to the site at the end of each cycle. The site personnel will ensure that the appropriate dose of each study drug is administered at each visit and will provide the patient with the correct amount of drug for subsequent dosing.

6.1.1 Dosing regimen

Table 6-1 Dose and treatment schedule

Study treatments	Pharmaceutical form and route of administration	Strength	Dose	Frequency and/or Regimen
LEE011	Capsule for oral use	200 mg/capsule	600 mg	Daily (21 days followed by one week break)
LEE011 matching Placebo	Capsule for oral use	N/A	N/A	Daily (21 days followed by one week break)

LEE011 and placebo will be supplied to investigational sites by Novartis or its designee as 200 mg hard gelatin capsules as individual patient supply packaged in bottles as double blind supply. Storage conditions are described on the medication label. Study drug will be taken orally, once a day for 21 consecutive days followed by a one week break as part of each 28-day cycle of treatment. The study drug will be administered as a flat-fixed dose, not by body weight or body surface area.

6.1.2 Study drug administration

Study drug should be taken as follows:

- Patients should be instructed to take his/her daily dose with a glass of water (~250 ml/8 oz.) in the morning at approximately the same time (+/- 1 hour). Patients may take study drug with or without food. Patients should be instructed to swallow capsules whole and not chew, crush or open, unless otherwise instructed. If patients cannot tolerate his/her daily dose in the morning, due to GI related side effects, then after cycle 1 it can be taken in the evening for the remainder of the study.
- [REDACTED]
- If vomiting occurs no re-dosing of the patient is allowed before the next scheduled dose.

[REDACTED]

- [REDACTED]
- Any doses that are missed (not taken within 6 hours of the intended time) should be skipped until the next day.

6.1.3 Guidelines for continuation of treatment

Not applicable

6.1.4 Treatment duration

Efficacy, safety and survival data will continue to be collected as per visit schedule (Table 7-1). Patients may continue treatment with study drug until disease progression as assessed by RECIST v1.1 (Appendix 1), occurrence of unacceptable toxicity that precludes any further treatment, or if treatment is discontinued at the discretion of the investigator or by patient's withdrawal of consent. Patients who progress on placebo may crossover to LEE011 and receive treatment until subsequent tumor progression, discontinuation at the discretion of the investigator or patient's withdrawal of consent (see Section 4.1.6). Patients receiving LEE011 may be allowed to continue treatment following progression if in the opinion of the investigator they are receiving clinical benefit. Details supporting continuation must be sent to Novartis for approval within 7 days of documented progression. For patients continuing on LEE011 after unblinding due to clinical benefit (not crossover patients), subsequent tumor assessments should be conducted according to local practice.

6.2 Dose modifications

6.2.1 Dose modification and dose delay

For patients who do not tolerate the protocol-specified dosing schedule, dose adjustments are permitted in order to allow the patient to continue the study drug. These changes must be recorded on the Dosage Administration Record eCRF. For patients undergoing a dose delay or reduction mid-cycle, upon restarting LEE011 during that cycle the, dosing should resume per the original cycle schedule. The planned 7-day break should begin on the originally planned date regardless of mid-cycle interruptions. Day 1 of subsequent cycles may be delayed if necessary to allow for toxicity resolution. If the study drug is delayed for more than 21 days due to drug toxicity, then study drug should be discontinued.

Severe or intolerable AEs may require dose reduction and/or interruption of study drug. Refer to Table 6-2 for guidance.

Table 6-2 Dose adjustments

Dose level	Daily dose	Frequency
*-2	200 mg	Daily (21 days), followed by one week break
*-1	400 mg	Daily (21 days), followed by one week break
1 (starting dose)	600 mg	Daily (21 days), followed by one week break

*Dose level-1 and -2 represent treatment doses for patients requiring a dose reduction from the starting dose level. No dose reduction below dose level -2 is permitted for this study.

[REDACTED]

Recommendations for dose reduction, interruption or discontinuation of study drug in the management of AEs are summarized in [Table 6-3](#). Clinical judgment of the treating physician and an individualized risk/benefit assessment should guide the management plan for each patient. A maximum of two study drug dose reductions (minimum dose is 200 mg) is allowed before study drug must be discontinued. Once a dose reduction has occurred, the dose level may not be re-escalated until the adverse event resolves to grade 1 and dose change has been authorized by the Novartis team.

Table 6-3 Study drug dose adjustment and management recommendation for hematological adverse reactions

[figure not shown]
Toxicity/Grade	Dose Adjustment and Management Recommendations
Thrombocytopenia	
Grade 1 ($\geq 75 \times 10^9/L$)	No dose adjustment required.
Grade 2 ($\geq 50 \times 10^9/L - < 75 \times 10^9/L$)	Dose interruption until recovery to grade ≤ 1 . Re-initiate study drug at the same dose.
Grade 3 ($\geq 25 \times 10^9/L - < 50 \times 10^9/L$)	Dose interruption until recovery to grade ≤ 1 . Re-initiate study drug at the same dose level. If toxicity recurs at grade 3: temporary dose interruption until recovery to grade ≤ 1 and reduce study drug to the next lower dose level.
Grade 4 ($< 25 \times 10^9/L$)	Dose interruption until recovery to grade ≤ 1 . Re-initiate study drug at the next lower dose level. If toxicity recurs at grade 4: discontinue study drug.
Absolute neutrophil count (ANC)	
Grade 1 ($\geq 1.5 \times 10^9/L$)	No dose adjustment required.
Grade 2 ($\geq 1.0 - < 1.5 \times 10^9/L$)	No dose adjustment required.
Grade 3 ($\geq 0.5 - < 1.0 \times 10^9/L$)	Dose interruption until recovery to $\geq 1.0 \times 10^9/L$. Re-initiate study drug at the same dose level. If toxicity recurs at grade 3: temporary dose interruption until recovery to $\geq 1.0 \times 10^9/L$. If resolved in ≤ 7 days, then maintain dose level. If resolved in > 7 days, then reduce study drug dose to the next lower dose level.
Grade 4 ($< 0.5 \times 10^9/L$)	Dose interruption until recovery to $\geq 1.0 \times 10^9/L$. Re-initiate study drug at the next lower dose level. If toxicity recurs at grade 4: temporary dose interruption until recovery to $\geq 1.0 \times 10^9/L$ and reduce study drug at the next lower dose level.
Febrile neutropenia	
Grade 3 ANC $< 1.0 \times 10^9/L$ with a single temperature of $> 38.3 \text{ }^\circ\text{C}$ ($101 \text{ }^\circ\text{F}$) or a sustained temperature of $\geq 38 \text{ }^\circ\text{C}$ ($100.4 \text{ }^\circ\text{F}$) for more than one hour	Dose interruption until improvement of ANC $\geq 1.0 \times 10^9/L$ and no fever. Restart at the next lower dose level. If febrile neutropenia recurs, discontinue study drug.
Grade 4 Life-threatening consequences; urgent intervention indicated	Discontinue study drug
Anemia (Hemoglobin)	
Grade 1 ($\geq 10.0 - \text{LLN g/dL}$)	No dose adjustment required.
Grade 2 ($\geq 8.0 - < 10.0 \text{ g/dL}$)	No dose adjustment required.
Grade 3 ($< 8.0 \text{ g/dL}$)	Dose interruption until recovery to grade ≤ 2 .

Toxicity/Grade	Dose Adjustment and Management Recommendations
	Re-initiate study drug at the same dose.
Grade 4 Life-threatening consequences; urgent intervention indicated	Discontinue study drug.

Table 6-4 Study drug dose adjustment and management recommendation for hepatic toxicities

HEPATOTOXICITY (BILIRUBIN, SGPT/ALT, SGOT/AST)	
TOTAL BILIRUBIN without ALT/AST increase above baseline value	
Grade 1 (> ULN – 1.5 x ULN) (confirmed 48-72h later)	Maintain dose level with LFTs monitored bi-weekly
Grade 2 (> 1.5 – 3.0 x ULN)	Dose interruption of study drug If resolved to ≤ grade 1 in ≤ 21 days, then maintain dose level If resolved to ≤ grade 1 in > 21 days or toxicity recurs, then reduce 1 dose level If toxicity recurs after two dose reductions, discontinue study drug
Grade 3 (> 3.0 – 10.0 x ULN)	Dose interruption of study drug If resolved to ≤ grade 1 in ≤ 21 days, lower 1 dose level of study drug If resolved to ≤ grade 1 in > 21 days or toxicity recurs, discontinue study drug
Grade 4 (> 10.0 x ULN)	Discontinue study drug
Confounding factors and/or alternative causes for increase of total bilirubin should be excluded before dose interruption/reduction. They include but are not limited to: evidence of obstruction, such as elevated ALP and GGT typical of gall bladder or bile duct disease, hyperbilirubinemia due to the indirect component only (i.e. direct bilirubin component ≤ 1 x ULN) due to hemolysis or Gilbert's Syndrome, pharmacologic treatment, viral hepatitis, alcoholic or autoimmune hepatitis, other hepatotoxic drugs. For patients with Gilbert's Syndrome, these dose modifications apply to changes in direct bilirubin only. Bilirubin will be fractionated if elevated.	
AST or ALT	
AST or ALT without bilirubin elevation > 2 x ULN	
Same grade as baseline or increase from baseline grade 0 to grade 1 (confirmed 48 – 72 h later)	No dose adjustment required with LFTs monitored per protocol if same grade as baseline or bi-weekly in case of increase from baseline grade 0 to 1
Increase from baseline grade 0 or 1 to grade 2 (> 3.0 – 5.0 x ULN) or from baseline grade 2 to grade 3 (> 5.0 – 20.0 x ULN)	Dose interruption of study drug If resolved to ≤ baseline value in ≤ 21 days, then maintain dose level If resolved to ≤ baseline value in > 21 days or toxicity recurs, then reduce 1 dose level If toxicity recurs after two dose reductions or recovery to ≤ baseline value is > 28 days, discontinue study drug
Increase from baseline grade 0 or 1 to grade 3 (> 5.0 – 20.0 x ULN)	Dose interruption of study drug until resolved to ≤ baseline value, then lower 1 dose level of study drug If recovery to ≤ baseline value is > 28 days, discontinue study drug If toxicity recurs, discontinue study drug
Grade 4 (> 20.0 x ULN)	Discontinue study drug
AST or ALT and concurrent Bilirubin	
AST or ALT ≥ grade 2 (> 3 x ULN) in patients with normal values at baseline and total bilirubin > 2 x ULN or	Discontinue study drug

HEPATOTOXICITY (BILIRUBIN, SGPT/ALT, SGOT/AST)	
AST or ALT \geq grade 3 ($> 5 \times$ ULN) in patients with grade 1 or 2 at baseline, and total bilirubin $> 2 \times$ ULN	
Confounding factors and/or alternative causes for increased transaminases should be excluded before dose interruption/reduction. They include but are not limited to: concomitant medications, herbal preparations or dietary supplements, infection, hepato-biliary disorder or obstruction, new or progressive liver metastasis, and alcohol intake.	

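### Section 6.2.1 and the grade 2 bilirubin row of Table 6-4 give opposite instructions from day 22 of a hold if calendar days off drug are counted, or if a scheduled Day 1 is itself held and moved

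*Protocol*

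**What the plan says.** Protocol Section 6.2.1 has one general time rule for toxicity: "If the study drug is delayed for more than 21 days due to drug toxicity, then study drug should be discontinued". No exception is visible.

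Table 6-4, in the same section, covers hepatic toxicity. For grade 2 total bilirubin without an ALT/AST increase, drug is interrupted. Recovery within 21 days keeps the dose level. For slower recovery the row reads: "If resolved to ≤ grade 1 in > 21 days or toxicity recurs, then reduce 1 dose level". It sets no upper time limit. For the same timing the grade 3 row reads: "If resolved to ≤ grade 1 in > 21 days or toxicity recurs, discontinue study drug". Two AST/ALT rows of the table discontinue only when recovery to baseline takes more than 28 days.

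Section 6.2.1 uses the idea of delay in two senses. One is a hold within a cycle: "For patients undergoing a dose delay or reduction mid-cycle". The other is a late start of a cycle: "Day 1 of subsequent cycles may be delayed if necessary to allow for toxicity resolution". It also fixes the week off: "The planned 7-day break should begin on the originally planned date regardless of mid-cycle interruptions". The visible text gives no rule for counting a delay.

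**The concern.** The general rule and the grade 2 row share a 21-day threshold and attach different outcomes to crossing it. The grade 3 row agrees with the general rule, so the grade 2 row reads as a distinct instruction.

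If the two clocks run together, a patient whose grade 2 bilirubin takes 22 days to recover should come off drug under one passage and restart one level lower under the other. Two sites could treat the same course differently, each relying on the protocol. The Amendment 2 rationale names a potential risk of hepatic toxicity with LEE011, so these are working safety instructions. The adverse event outputs on drug discontinuation and dose adjustment (SAP 3.6.1) could depend on which passage a site followed.

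**Working it through.** The plan states no figure to reproduce. The check asks on which day of a hold the passages part, for each meaning that delay could have.

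**Inputs.** The cycle is 21 dosing days and 7 days off (Protocol 6.1.1). The general rule triggers at a delay above 21 days (6.2.1). The grade 2 bilirubin row changes from maintain to reduce at a resolution time above 21 days (Table 6-4).

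**Notation.** d is the cycle day of the first withheld dose (1 to 21). L is calendar days off drug. R is days to resolution. a is the number of days from the start of the resolution clock to interruption. Assumption: dosing restarts at recovery, so L = R - a. The base case takes a = 0.

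**First hold day on which delay exceeds 21**

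| Meaning of delay | Delay as a function of L | First L above 21 |
|---|---|---|
| Calendar days off drug | L | 22 |
| Day 1 itself held and moved | L | 22 |
| Missed scheduled doses | dosing days within the hold | 29 |
| Slippage of next Day 1 after a mid-cycle hold | d + L - 29 | 51 - d |

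- Missed doses: any 28-day window holds 21 dosing days. The count is 21 at L = 28 and first reaches 22 at L = 29, for every d.
- Mid-cycle slippage: the next Day 1 is planned for day 29 and restart falls on day d + L. Requiring d + L - 29 to be at least 22 gives L = 51 - d: 49 at d = 2, 43 at d = 8, 36 at d = 15 and 30 at d = 21.

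**Side by side at a = 0.** At L = 21 the row says maintain and 6.2.1 is not triggered. At L = 22 the row says reduce one level; on the first two counts 6.2.1 says discontinue, and this continues for every longer hold. On the missed-dose count both can be followed for R = 22 to 28. On the mid-cycle slippage count both can be followed for R = 22 to 50 - d, that is 22 to 29 at d = 21 and 22 to 48 at d = 2.

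**Break days in the calendar count.** At L = 22 the hold includes min(d, 7) planned break days, so 1 to 7. Missed doses are then 22 - 1 = 21 at d = 1, falling to 22 - 7 = 15 for d of 7 or more.

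**Start of the resolution clock.** Table 6-4 does not say when it starts, and interruption may come after onset: "Confounding factors and/or alternative causes for increase of total bilirubin should be excluded before dose interruption/reduction". On the first two counts the conflict then begins at R = 22 + a. For an assumed a of 0 to 7 days this is day 22 to day 29. A restart b days after recovery changes it to R = 22 + max(0, a - b).

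**AST/ALT rows with the 28-day limit.** On the first two counts these conflict with 6.2.1 for R = 22 + a to 28. That is days 22 to 28 at a = 0, day 28 only at a = 6, and none at a = 7. There is no conflict on missed doses (21 by day 28) or on mid-cycle slippage (at most 21 + 28 - 29 = 20 by day 28).

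**The case against.** The strongest reply is that 6.2.1 is a general cap over every row. Nine other rows interrupt until recovery with no time limit (seven in Table 6-3, two in Table 6-6), and they sit well under a cap. This reconciles the passages on the missed-dose and mid-cycle slippage counts, where slow recovery can lead to a reduction before the cap bites. It fails on the other two counts: at a = 0, every case reaching the time-based reduction would already have to stop, so that branch could never be used.

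A second reply is that the calendar count is strained for mid-cycle holds. It counts planned break days as toxicity delay, and the 21-day sentence directly follows the one about a late Day 1. Also, with a hold from cycle day 2 to 6 and R = 22, recovery falls on days 24 to 28, inside the break, so no dose is yet due. This has force. It leaves untouched the case where a scheduled Day 1 is held and moved by 22 days.

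Third, the Amendment 2 rationale says the hepatobiliary guidance was separated from that for other adverse events. That bears on intent, but it is not a precedence rule. A redacted block in 6.2.1 cannot be checked.

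Fourth, the section says "Recommendations for dose reduction, interruption or discontinuation of study drug in the management of AEs are summarized in" Table 6-3. A reader might infer that Table 6-4 stands outside 6.2.1. It does not: it follows Table 6-3 within that section, so nothing here rests on the missing reference.

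**Conclusion.** The inconsistency is real, and its effect is limited. On a calendar count, or when a scheduled Day 1 is itself held and moved, the instructions for grade 2 bilirubin are opposite from day 22 of the hold, and the AST/ALT rows also conflict with 6.2.1 on days 22 to 28. Both statements assume that the resolution clock starts with the hold and that dosing restarts at recovery. Otherwise divergence starts at day 29 (missed doses) or at hold day 30 to 49 (mid-cycle slippage), and on those counts a cap reading removes it.

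Three stronger readings are not supported:

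- A reader might infer that any count of a moved Day 1 gives day 22. That holds only when the hold starts on a scheduled Day 1.
- A reader might infer that the reporting would hide such a case, since SAP Section 4 drops the reasons for dose interruption, reduction and change. But action taken is recorded for each adverse event (Protocol 8.1.1), outputs on discontinuation and dose adjustment are kept (SAP 3.6.1), and liver function values are listed (SAP 3.6.3). A case could largely be reconstructed.
- A reader might infer that patients were handled inconsistently. No such case is documented. Ten patients were enrolled and 4 were on treatment at 18-Aug-2017, 3 of them still blinded.

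The wording is advisory and leaves room for clinical judgment. No efficacy result depends on it, because SAP Section 4 drops the efficacy analyses.

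**What to change.** Reconcile the 21-day sentence in Section 6.2.1 with the grade 2 bilirubin row of Table 6-4, and with the two AST/ALT rows that carry the 28-day limit. State how a delay is counted (calendar days, missed doses or movement of Day 1), when the resolution clock starts, and which passage governs hepatic events. Notify any site that still has patients on treatment. The sponsor's clinical team decides the content; no limit is proposed here.

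The cost is a protocol wording change and a short clarification letter. No analysis changes.

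### Table 6-4 (hepatic toxicity): for ALT/AST rises below the concurrent-elevation threshold the three sections do not fit together, so some results match no row and others lose the interruption instruction

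*Protocol*

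**What the plan says.** Table 6-4 is in Protocol section 6.2.1. For reference, its sections are called A, B and C here.

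- **A, bilirubin rows.** Entry condition: "TOTAL BILIRUBIN without ALT/AST increase above baseline value". Within A, "Grade 2 (> 1.5 – 3.0 x ULN") calls for interruption. "Grade 3 (> 3.0 – 10.0 x ULN") calls for interruption followed by a lower dose level or discontinuation. "Grade 4 (> 10.0 x ULN") calls for discontinuation.
- **B, ALT/AST rows.** Entry condition: "AST or ALT without bilirubin elevation > 2 x ULN". The mildest row, "Same grade as baseline or increase from baseline grade 0 to grade 1", requires no dose adjustment, with liver tests as scheduled if the grade is unchanged and bi-weekly after a move from grade 0 to 1.
- **C, concurrent elevation.** The action is to discontinue. It applies to ALT/AST of grade 2 or more (above 3 x ULN) "in patients with normal values at baseline and total bilirubin > 2 x ULN". It also applies to ALT/AST of grade 3 or more (above 5 x ULN) "in patients with grade 1 or 2 at baseline, and total bilirubin" above 2 x ULN.

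Patients with raised baseline transaminases can enter the study. Exclusion criterion 15 in section 5.3 bars AST/ALT above 2.5 x ULN, or at or above 5 x ULN with liver metastases.

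**The concern.** Section A closes once ALT/AST rises above baseline, and section B closes once bilirubin passes 2 x ULN. Section C opens only when ALT/AST passes a further threshold. A patient whose ALT/AST has risen, but not that far, may therefore have left A without qualifying for B or C. Alternatively, the patient may land in a row of B that takes no account of bilirubin up to 2 x ULN.

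The Amendment 2 rationale gives the reason for the hepatic guidance as possible drug-induced liver injury, seen as a transaminase rise alone or together with a bilirubin rise. The combined pattern is where the sections fail to join. Two sites with the same blood results could act differently and both claim to follow the table. The close observation in section 6.2.1.1 is also tied to a rise that requires interruption, so a patient sent to no adjustment, or to no row, loses that trigger as well.

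**Working it through.** No sample size or power figure is involved. The check applies the three entry conditions to example results.

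**Inputs.** All cut-offs are those of Table 6-4. One assumption is added: ALT/AST grade 1 runs from above ULN to 3.0 x ULN, inferred from the table's lower bound for grade 2.

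**Two readings.** The increase above baseline value in A's heading can mean any numeric rise, or a rise in CTCAE grade. Both were tried.

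Letters show which section supplies the action; all values are multiples of ULN.

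| Baseline ALT | Current ALT | Bilirubin 1.8 | Bilirubin 2.5 | Bilirubin 5 | Bilirubin 12 |
|---|---|---|---|---|---|
| 0.8 | 0.8 | interrupt (A) and no adjustment (B) | interrupt (A) | interrupt, then lower or stop (A) | discontinue (A) |
| 0.8 | 1.5 or 2.5 | no adjustment (B) | no row | no row | no row |
| 0.8 | 4.0 | interrupt (B) | discontinue (C) | discontinue (C) | discontinue (C) |
| 2.0 | 2.0 | interrupt (A) and no adjustment (B) | interrupt (A) | interrupt, then lower or stop (A) | discontinue (A) |
| 2.0 | 4.0 or 4.8 | interrupt (B) | no row | no row | no row |
| 2.0 | 8 | interrupt, then lower (B) | discontinue (C) | discontinue (C) | discontinue (C) |
| 4.0 | 4.4 or 4.8 (numeric reading only) | no adjustment (B) | no row | no row | no row |
| 4.0 | 8 | interrupt (B) | discontinue (C) | discontinue (C) | discontinue (C) |

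**Result 1, no row.** Take a normal baseline, ALT 2.5 and bilirubin 12. A fails because ALT has risen, B fails because 12 > 2, and C fails because 2.5 is not above 3. The same bilirubin with ALT unchanged is in A and means discontinue. For baseline grade 1 with ALT at 4.0, C fails because 4.0 is not above 5. The gap is bilirubin above 2 x ULN with ALT/AST above baseline but at or below 3 x ULN (normal baseline) or 5 x ULN (baseline grade 1 or 2).

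**Result 2, conflict, then loss of the interruption.** At bilirubin 1.8 with ALT unchanged, A's grade 2 row and B's mildest row both apply, with different actions. For a patient whose ALT was and stays normal, this treats grade 0 as a grade, as that row itself does. When ALT then rises from 0.8 to 1.5 (grade 0 to 1), A closes and only B's no adjustment is left. The zone is bilirubin above 1.5 and up to 2.0 x ULN.

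**Dependence on the reading.** The moves from 0.8 to 1.5 or 2.5, and from 2.0 to 4.0 or 4.8, are rises in grade, so both results hold under either reading. Rises within a grade, such as 4.0 to 4.4, lose their row only under the numeric reading. Under the grade reading they count as unchanged.

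**The case against.** Four points can be made for the table.

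1. **It does escalate.** With bilirubin above 2 x ULN and ALT/AST above the section C thresholds, the action is discontinuation, the strongest in the table. A reader might infer that any worsening of ALT/AST alongside raised bilirubin weakens the instruction; the documents do not support that. This point stands and limits the finding to rises below the thresholds.

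2. **The starting point is not a clear interruption.** At bilirubin 1.8 x ULN with ALT unchanged, two rows already apply. It is tempting to describe a clean move from interrupt to no adjustment, but the text shows a conflict first and then the loss of one side of it. One may also read B's mildest row as speaking about transaminases only. That would ease the conflict while ALT is unchanged. It does not reopen section A once ALT has risen.

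3. **There are fallbacks.** Section 6.2.1 calls the tables recommendations and leaves management to clinical judgment. Section 7.1.3 tells the investigator to stop treatment if continuing would be detrimental. Table 6-6 gives grade-based actions for other adverse reactions, including discontinuation at grade 4. So a reader should not infer that a patient with extreme bilirubin is left without any protocol direction. These provisions may soften the effect. However, none supplies the missing row, and nothing sends hepatic tests to Table 6-6.

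4. **Few patients are affected.** The Amendment 3 status note reports enrollment halted on 20-Nov-2015 with 10 patients enrolled. On 18-Aug-2017, 4 were on treatment: 3 blinded and 1 already crossed over. This stands as a limit on size. The table still governs those patients, and any placebo patient among the 3 blinded may start LEE011.

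A share of unmatched combinations could also be quoted, but it would describe the chosen grid and reading, not how often patients meet the gap.

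**Conclusion.** The finding holds as an internal inconsistency in Table 6-4, confined to ALT/AST rises below the concurrent thresholds. With bilirubin above 2 x ULN such rises match no row. With bilirubin above 1.5 and up to 2.0 x ULN the table gives two actions while ALT/AST is unchanged, and only the milder one after a rise from grade 0 to 1. The conclusion rests on the section headings as worded and on the inferred grade 1 range for ALT/AST, and it survives both readings of an increase above baseline.

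The documents give no frequency for these patterns, so the effect cannot be expressed as a number of patients beyond the 4 on treatment. It still merits correction: a site following the table exactly can meet conflicting, weaker or absent instructions for a recognised liver risk.

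**What to change.** Amend Table 6-4 so that the three section headings and their bilirubin and ALT/AST cut-offs are reconciled. Every combination of baseline ALT/AST, current ALT/AST and bilirubin should fall in exactly one row, and no worse combination should receive a weaker instruction. State whether an increase above baseline means a numeric rise or a rise in grade. Which action belongs in each cell is for the sponsor's clinical team; none is proposed here.

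The cost is the rewording of one table, with no new tests or patients. Section 12.1 requires a written protocol amendment with IRB/IEC approval, and health authority approval where needed, so an investigator letter alone would not be enough. The same section allows an amendment required for patient safety to be implemented before IRB/IEC approval.

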6.2.1.1 Additional follow-up for hepatic toxicities

Hepatic toxicity monitoring includes the following LFTs: albumin, ALT, AST, total bilirubin (fractionated if total bilirubin $> 2 \times$ ULN), alkaline phosphatase (fractionated if alkaline phosphatase is grade 2 or higher) and GGT. For patients with Gilbert’s Syndrome: total and direct bilirubin must be monitored, intensified monitoring applies to changes in direct bilirubin only.

Close observation is recommended in case of AST, ALT, and/or bilirubin increase requiring dose interruption, which involves:

[figure not shown]
- Repeating liver enzyme and serum bilirubin tests **two or three times weekly**. Frequency of re-testing can decrease to once a week or less if abnormalities stabilize or return to normal values.
- Obtaining a more detailed history of current symptoms.
- Obtaining a more detailed history of prior and/or concurrent diseases.
- Obtaining a history of concomitant drug use (including non-prescription medications, herbal and dietary supplements), alcohol use, recreational drug use, and special diets.
- Ruling out acute viral hepatitis types A, B, C, D, and E; hepatotropic virus infections (Cytomegalovirus (CMV), Epstein Barr Virus (EBV) or Herpes Simplex Virus (HSV); autoimmune or alcoholic hepatitis; non-alcoholic steatohepatitis (NASH); hypoxic/ischemic hepatopathy; and biliary tract disease.
- Obtaining a history of exposure to environmental chemical agents.
- Obtaining additional tests to evaluate liver function, as appropriate (e.g., INR, direct bilirubin).
- Considering gastroenterology or hepatology consultations.

Assessing cardiovascular dysfunction or impaired liver oxygenation, including hypotension or right heart failure as possible etiologies for liver dysfunction.

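### Table 6-4 calls for interruption at grade 2-3 liver test rises, but its notes put exclusion of other causes first, with no deadline or interim hold

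*Protocol*

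**What the plan says.** Table 6-4 (Protocol Section 6.2.1) sets out dose changes for hepatic toxicity. Four of its rows open with an interruption: bilirubin grade 2, bilirubin grade 3, AST/ALT rising from baseline grade 0-1 to grade 2 (or from 2 to 3), and AST/ALT rising from baseline grade 0-1 to grade 3. The last of these, for example, begins "Dose interruption of study drug until resolved to" the baseline value. Below these levels dosing continues under closer testing; for bilirubin grade 1 the instruction is "Maintain dose level with LFTs monitored bi-weekly".

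Two notes qualify the rows. The bilirubin note reads "Confounding factors and/or alternative causes for increase of total bilirubin should be excluded before dose interruption/reduction". The transaminase note reads "Confounding factors and/or alternative causes for increased transaminases should be excluded before dose interruption/reduction". Causes to be considered include, for bilirubin, "pharmacologic treatment, viral hepatitis, alcoholic or autoimmune hepatitis, other hepatotoxic drugs" and, for transaminases, "infection, hepato-biliary disorder or obstruction, new or progressive liver metastasis, and alcohol intake". For Gilbert's Syndrome the bilirubin note adds that "these dose modifications apply to changes in direct bilirubin only".

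Section 6.2.1.1 then describes the follow-up: "Close observation is recommended in case of AST, ALT, and/or bilirubin increase requiring dose interruption, which involves" repeat liver tests two or three times weekly, detailed histories, and the ruling out of viral, autoimmune and alcoholic hepatitis and biliary disease.

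**The concern.** Row and note put the same two steps in different orders. The row says to interrupt at this level. The note says that interruption should come after other causes have been excluded. A site that gives the note precedence has no stated limit on how long the exclusion may take and no instruction to hold drug during it.

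What is at stake is patient safety. The rationale for Amendment 2 gives the reason for the separate hepatic guidance: a potential risk of drug-induced liver injury, seen as transaminase rises alone or together with bilirubin. Isolated AST/ALT rises of > 3 to 20 x ULN are therefore part of the signal the table was written for, and they are the rises whose interruption the transaminase note can delay. That rationale does not name isolated bilirubin rises. The bilirubin note also handles benign explanations directly, so for the two bilirubin rows the point is mostly the conflict of wording.

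**Working it through.** No arithmetic decides this point. The check is to set the texts side by side.

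**1. Rows against notes**

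| Row of Table 6-4 | Level (x ULN) | Action in row | Condition on cause in row | Note that reaches it |
|---|---|---|---|---|
| Bilirubin grade 2 | > 1.5 to 3.0 | interrupt | none | bilirubin note |
| Bilirubin grade 3 | > 3.0 to 10.0 | interrupt | none | bilirubin note |
| AST/ALT grade 0-1 to 2, or 2 to 3 | > 3.0 to 5.0, or > 5.0 to 20.0 | interrupt | none | transaminase note |
| AST/ALT grade 0-1 to 3 | > 5.0 to 20.0 | interrupt | none | transaminase note |
| Grade 4, or AST/ALT with bilirubin > 2 x ULN | as defined in the table | discontinue | none | neither |

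The rows do carry other conditions. The AST/ALT rows depend on baseline grade and on bilirubin not exceeding 2 x ULN, and the bilirubin rows on no AST/ALT increase above baseline. None depends on cause. The transaminase note is printed under the combined row, whose only action is discontinuation, so its reference to interruption or reduction must be to the AST/ALT rows above.

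**2. Is there a deadline or a hold elsewhere?** None was found in Table 6-4 or Section 6.2.1.1. The 48-72 hour confirmation belongs only to the lowest rows, where no dose change is made.

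**3. Does Section 6.2.1.1 settle the order?** No. It ties the work-up to a rise that requires interruption. Under the notes, interruption waits for the exclusion of causes; under 6.2.1.1, much of that exclusion accompanies an interruption. If the note is followed, it is also unclear whether the retesting two or three times weekly has been triggered.

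**4. Can the exclusion be done at once?** Partly. Medication, herbal product and alcohol histories can be taken the same day, and bilirubin fractions are in the chemistry panel (Table 7-3). Viral or autoimmune hepatitis, infection, obstruction and new liver metastasis need further tests or imaging.

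**5. How does the protocol order these steps elsewhere?** Table 6-5 interrupts first for QTc grade 2 and repeats the ECG one hour later. For abnormal electrolytes it interrupts and then corrects.

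**6. Size.** Dosing is once daily on Days 1-21 of each cycle, so each dosing day spent on the work-up without a hold adds one dose. The number of such days is not given, so the total cannot be derived.

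**The case against.** The strongest reply is that the protocol nowhere says dosing continues during the work-up. Read with the rows, Section 6.2.1.1 can be taken to mean that interruption and investigation go together. The notes say should, and the table is titled as a recommendation. Section 6.2.1 puts clinical judgment first, and Section 7.1.3 says the investigator should stop treatment believed to be detrimental. The most dangerous patterns go straight to discontinuation. Liver tests also have many non-drug causes, so an attribution step is a defensible way to avoid needless dose loss. All of this stands, and it lowers the priority. It does not remove the conflict, because these clauses permit an early hold without requiring one.

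A reader might infer three stronger things that the documents do not support:

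- **That sites are instructed to keep dosing.** They are not; this is only what a literal reading of the notes allows.
- **That the work-up must be slow, because the routine panel lacks GGT and hepatitis tests and scans are 8-weekly in the first year.** Section 6.2.1.1 lists GGT among the hepatic monitoring tests, Section 7.2.1 allows earlier tumor evaluation when progression is a clinical concern, and Section 7.2.2.5 allows more frequent laboratory tests.
- **That the extra dose can be stated in milligrams.** Any such figure would only multiply an assumed work-up time.

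Nor does Table 6-6, which interrupts at grade 2 with no exclude-first step, prove much. It covers all other adverse reactions and can be read as applying to events already attributed to the drug.

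**Conclusion.** The point holds as a conflict in the order of steps: four rows call for interruption, two notes place exclusion of causes before it, and no deadline or interim hold is given. It matters mainly for the two AST/ALT rows.

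The safety consequence rests on one assumption, that a site reads the word before in the notes literally. The extra exposure is not quantifiable from the documents. Reach is small: Amendment 3 reports 10 patients enrolled and 4 on treatment at 18-Aug-2017, 3 of them still blinded and 1 crossed over. It also allows placebo patients to cross over to LEE011, so reach is not zero. The text available reports no liver event in these patients. Priority: low.

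**What to change.** Replace the first sentence of both notes with wording such as:

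> *Study drug is interrupted when the stated grade is reached; do not delay interruption pending results. Confounding factors and/or alternative causes are investigated promptly during the interruption (Section 6.2.1.1). If an alternative cause is documented, the investigator may restart study drug by clinical judgment, and the dose reduction or discontinuation in the row need not apply.*

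State that this covers only the four interruption rows, so that grade 4 and combined rises still lead to discontinuation. Keep the lists of causes and the Gilbert's rule. Add that no interruption is required when a bilirubin rise is confined to the indirect component (direct bilirubin no more than 1 x ULN) and is due to documented hemolysis or Gilbert's Syndrome. In Section 6.2.1.1, start the close observation when a result reaches a grade for which Table 6-4 lists interruption.

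Restart should not be tied to the row's recovery criterion once a non-drug cause is documented. That could end treatment for reasons unrelated to the drug, in a disease for which Section 1.1.3 says no standard therapy exists. It would also go beyond the general stopping rule in Section 6.2.1, which covers delays of more than 21 days due to drug toxicity.

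The cost is some short interruptions for rises not caused by the drug. No test is added beyond those the protocol already lists. The change needs a written amendment with the approvals in Section 12.1.
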